#### 4.3.2.2. Main Analytical Approach for Categorical Measures

For the percentage of participants achieving at least 5% body weight reduction from randomization over time, a logistic regression model will be used with the response variable of the percentage of participants achieving at least 5% body weight reduction at each scheduled postbaseline visit.

A logistic regression model with terms of treatment group stratification factors: baseline IGT (yes or no); baseline hyperlipidemia (based on TG; yes or no); baseline NAFLD (yes or no) and sex (female, male) as fixed effects, and baseline body weight as a covariate, will be conducted for percentage of participants achieving at least 5% body weight reduction from randomization at the 72 week visit. Missing body weight measurement at 72 week will be imputed by the predicted value from MMRM model aforementioned, then the continuous measurements will be dichotomized into status of achieving at least 5% body weight reduction (Yes or No). A logistic regression will be utilized to analyze proportion of participants with at least 5% body weight reduction at each nominal visit from randomization through 72 weeks.

With the aid of the logistic regression model, 2-sided 95% CI and odds ratio for percentage of participants achieving at least 5% body weight reduction from baseline to the 72-week visit between tirzepatide 10 mg or 15 mg QW and placebo will be derived.

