9.4.3. Efficacy Analyses

9.4.3.1. Primary Analyses

The primary efficacy analysis will be guided by the "efficacy" estimand, which represents efficacy prior to discontinuation of study drug under missing at random assumption. The efficacy analyses will be conducted using the EAS. The primary analysis model will be a MMRM for body weight percentage change over time and longitudinal logistic regression for proportion of participants achieving at least 5% body weight reduction over time. The response variable of MMRM will be the percent change in body weight from baseline values obtained at each scheduled postbaseline visit. The response variable of longitudinal logistic regression will be the achievement of at least 5% body weight reduction at each scheduled postbaseline visit. The independent variables of both analysis models are treatment group (tirzepatide 10 mg, tirzepatide 15 mg, and placebo), visit, and treatment by visit interaction, stratification factors: baseline IGT (yes or no); baseline hyperlipidemia (based on TG; yes or no); baseline NAFLD (yes or no) and sex (female, male), and baseline body weight as a covariate. An unstructured covariance structure will model relationship of within-patient errors. The Kenward-Roger approximation will be used to estimate denominator degrees of freedom. Since the mean percent change in body weight and the percentage of participants with $\geq 5\%$ body weight reduction needs to be achieved at the same time, no multiplicity adjustment is planned for these 2 tests.

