# 1. Introduction

Changes to the protocol-planned analyses are described in Section 4.9.

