#### 2.1. Multiplicity Adjustment

The type 1 error will be controlled in the strong sense at a two-sided significance level of 0.05 because two hypotheses ( $H_{10}$  and  $H_{15}$ ) will be tested in parallel each at a 2-sided significance level of 0.025. Since superiority of each one of two hypotheses will be declared if and only if both statistical tests (regarding percent change in body weight and percentage of participants who achieve  $\geq$ 5% body weight reduction) are significant, no multiplicity adjustment is planned for these 2 tests.

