Analysis Dataset	Analysis Type	Baseline	Postbaseline
SS	1.1) Treatment-Emergent Adverse Events	The baseline period is defined as the start of screening and ends prior to the first dose in of study treatment (typically at Week 0).	Starts after the first dose of study treatment and ends at the end of the study period (including off-drug follow up visit).
SS	1.2) Treatment-Emergent Abnormal Labs a , Vital Signs, and ECGs.	Baseline will include all scheduled and unscheduled measurements during the baseline period (Visit 1 to Visit 3)	Postbaseline will be defined as above (1.1). All scheduled and unscheduled measurements will be included.
SS	1.3) Change from Last Baseline to Week xx and to Last Postbaseline for Labs a ,Vital Signs, and ECGs.	The last scheduled and unscheduled non-missing assessment recorded during the baseline period defined above (1.2).	Postbaseline will be defined as above (1.1). Only scheduled visits will be included. The early discontinuation (ED) visits are considered scheduled visits.

Table GPHZ.4.1. Baseline and Postbaseline Definitions for Safety Analysis

Abbreviations: ECGs = electrocardiogram; SS = Safety Analysis Set.

For the primary and secondary efficacy endpoint analyses, data for participants with missing values at the 72-week visit will be imputed based on the method described in Section 4.3.2. Otherwise, missing values will not be explicitly imputed except for the parameters with only 1 postbaseline measure during the analysis period per schedule of activity, where last observation carried forward (LOCF) approach will be applied to impute the endpoint when ED measure is available.

End of study participation for a participant will be the earliest of date of death, date of withdrawal from further participation in the study, or date of safety follow-up visit (Visit 801). For participants considered to be lost-to-follow-up, end of study participation will be the date of lost-to-follow-up reported by the investigator. Participant data included in the database after the last date of study participation (including safety follow-up period) will be excluded from statistical analysis.

Statistical treatment comparisons will only be performed between tirzepatide 10 mg or 15 mg, and placebo. Since the trial is not adequately powered to detect difference among tirzepatide doses, comparisons among tirzepatide doses will not be performed unless otherwise specified.

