#### 4.3.3. Supplementary analyses

#### 4.3.3.1. Analysis Related to the Treatment Regimen Estimand

The analysis related to the "treatment-regimen" estimand will be conducted using data in the FAS.

The analysis for the mean percent change in body weight will be conducted utilizing ANCOVA. The response variable for the ANCOVA model will be percent change in body weight from randomization to Week 72. This model will include terms of baseline IGT (yes or no); baseline hyperlipidemia (based on TG; yes or no); baseline NAFLD (yes or no) and sex (female, male) as fixed effects and baseline body weight as a covariate. The ANCOVA analysis will be conducted with multiple imputation of missing body weight at Week 72 and statistical inference over multiple imputation of missing data guided by Rubin (1987).

With the aid of the ANCOVA model, 2-sided 95% CI for mean change in percent body weight from baseline to the 72-week visit between tirzepatide 10 mg or 15 mg QW and placebo will be derived.

With the aid of the logistic regression model, 2-sided 95% CI and odds ratio for percentage of participants achieving at least 5% body weight reduction from baseline to the 72-week visit between tirzepatide 10 mg or 15 mg QW and placebo will be derived.

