Percentage of participants who met the following criteria at 72 weeks from BL	Improvement in at 2 or 3 obesity related health problems	Efficacy analysis set - participants with 3 defined obesity-related health problems	Logistic model in Section 4.3.2.2	Exploratory
	Improvement in at 2 obesity related health problems	Efficacy analysis set - participants with 2 defined obesity-related health problems	Logistic model in Section 4.3.2.2	Exploratory
	Improvement in at 1 obesity related health problems	Efficacy analysis set - participants with 3 defined obesity-related health problems	Logistic model in Section 4.3.2.2	Exploratory

Abbreviations: ANCOVA = analysis of covariance; BL = baseline; BMI = body mass index; IGT = impaired glucose tolerance; MMRM = mixed model for repeated measures; NAFLD = non-alcoholic fatty liver disease; OGTT = oral glucose tolerance test; TG = triglycerides; TZP = tirzepatide.

Table GPHZ.4.3. Secondary and Exploratory Efficacy Measures for Body Mass

Analysis variable	Criteria/Measures	Analysis set	Analysis method	Additional Information
Change in body weight (24, 52, and 72 weeks)	Proportion of participants who achieve the following criteria from BL	Efficacy analysis set	Logistic model in Section 4.3.2.2	
	
 
≥5% body weight reduction (only at 24 and 52 weeks)
 
≥7% body weight reduction
 
≥10% body weight reduction
 
≥15% body weight reduction
 
≥20% body weight reduction
 
			
	Mean percent change from BL in  • Body weight (%) (Only at 24 and 52 weeks)	Efficacy analysis set	MMRM model in Section 4.3.2.1	
	Mean change from BL in			
	

Absolute body weight (kg)

BMI

			
EWL	EWL defined in Section 4.4.1.1	Efficacy analysis set	MMRM model in Section 4.3.2.1	
Change in VAT and SAT (72 weeks)	Mean change from BL in  VAT area (cm²)  SAT area (cm²)  VAT/SAT ratio	Efficacy analysis set	ANCOVA model in Section 4.4.2.1	
	Mean percent change from BL in  VAT area (cm²)  SAT area (cm²)  VAT/SAT ratio	Efficacy analysis set	ANCOVA model in Section 4.4.2.1	

Analysis variable	Criteria/Measures	Analysis set	Analysis method	Additional Information
	Proportion of participants who achieve VAT <100 cm 	Efficacy analysis set - participants with VAT ≥100 cm² at	Logistic model in Section 4.4.2.2	
Change in waist circumference (24, 52, and 72 weeks)	Mean change from BL in waist circumference	BL Efficacy analysis set	MMRM model in Section 4.3.2.1	

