# 4.9. Changes to Protocol-Planned Analyses

Efficacy analysis set for imaging data has been modified to accommodate the allowance of measurement schedule.

Added following exploratory objectives:

- Improvement of hyperuricemia (defined by uric acid ≤7.0 mg/dL).
- Improvement of hypertension: Diastolic blood pressure <80 mmHg or Systolic blood pressure <130 mmHg.
- Achievement of ALT ≤30 U/L.
- Changes in NAFLD fibrosis score.

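### SAP 4.3.2.2 fills missing Week 72 weights with the MMRM predicted value before cutting at 5%, which overstates the responder difference and odds ratio at the plan's own 25% versus 90%

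*SAP*

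**What the plan says.** SAP 4.3.2.2 is the main analysis of the second co-primary endpoint under the efficacy estimand. It fits an ordinary logistic regression to the ≥5% responder status at Week 72, and deals with missing data in this way: "Missing body weight measurement at 72 week will be imputed by the predicted value from MMRM model aforementioned, then the continuous measurements will be dichotomized". It mentions no residual draw, no repeated imputation and no pooling.

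The rule reaches beyond this endpoint. SAP 4.1 states for primary and secondary efficacy endpoints that "data for participants with missing values at the 72-week visit will be imputed based on the method described in Section 4.3.2". Table GPHZ.4.3 sends the ≥7%, ≥10%, ≥15% and ≥20% thresholds to the "Logistic model in Section 4.3.2.2".

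Multiple imputation with Rubin's rules is planned, but only for the treatment-regimen estimand (SAP 4.3.3.1 and 4.3.3.2).

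Protocol 9.4.3.1 had specified a different method for this endpoint: "longitudinal logistic regression for proportion of participants achieving at least 5% body weight reduction over time". SAP section 1 says "Changes to the protocol-planned analyses are described in Section 4.9". Section 4.9 lists the imaging-window change ("Efficacy analysis set for imaging data has been modified to accommodate the allowance of measurement schedule") and some added exploratory objectives, but not this one.

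**The concern.** A model prediction is an expected value, so it carries less spread than the outcome it stands for. If a whole arm's missing weights are replaced by predictions, too many fall on the same side of the 5% threshold as the arm mean. An arm with a true responder rate below 50% gets an imputed rate that is too low, and an arm above 50% gets one that is too high. The plan expects 25% on placebo and 90% on tirzepatide, so both errors favour tirzepatide.

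The analysis then treats the completed data as fully observed. At the planned dropout about 87 participants per arm are analysed, although only about 65 have a Week 72 value, so the standard error is also too small.

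At stake are the odds ratio and 95% CI that SAP 4.3.2.2 asks for, and the difference in response percentage that SAP 1.1.2.1 names as the population-level summary.

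**Working it through.** **Inputs.** From SAP section 5 and Protocol 9.2: 87 per arm, two-sided 0.025 per dose, 25% dropout; placebo 25% and tirzepatide 90% responders; for the continuous endpoint an 11-point difference with SD 10. The correlation R between the MMRM prediction and the true Week 72 value is not in the documents; I assume 0.5 to 0.95.

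**Step 1: the plan's power.** With 87 × 0.75 ≈ 65 per arm, power is 0.99996 for the t-test and above 0.99999 for Fisher's exact test. Both agree with the stated figure of more than 90%.

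**Step 2: closed form.** Let change in an arm be normal with mean μ and SD σ, and let missingness be unrelated to outcome. The true rate is p = Φ(z), with z = (−5 − μ)/σ. The prediction has mean μ and SD Rσ, so a missing participant is scored a responder with probability Φ(z/R) instead of Φ(z). The analysed arm rate is

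0.75·p + 0.25·Φ(Φ⁻¹(p)/R).

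Here z = −0.674 for placebo and 1.282 for tirzepatide. At R = 0.7:

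- placebo: Φ(−0.674/0.7) = 0.1676; 0.75 × 0.25 + 0.25 × 0.1676 = 0.229
- tirzepatide: Φ(1.282/0.7) = 0.9664; 0.75 × 0.90 + 0.25 × 0.9664 = 0.917

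| R | Placebo | Tirzepatide | Difference (points) | Bias | OR |
|---|---|---|---|---|---|
| 1 (truth) | 25.0% | 90.0% | 65.0 | 0 | 27.0 |
| 0.95 | 24.7% | 90.3% | 65.6 | +0.6 | 28.3 |
| 0.9 | 24.4% | 90.6% | 66.1 | +1.1 | 29.7 |
| 0.8 | 23.7% | 91.1% | 67.4 | +2.4 | 33.0 |
| 0.7 | 22.9% | 91.7% | 68.7 | +3.7 | 36.9 |
| 0.5 | 21.0% | 92.4% | 71.4 | +6.4 | 45.6 |
| 0 (arm mean only) | 18.8% | 92.5% | 73.8 | +8.8 | 53.4 |

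With 10% missing instead of 25%, the bias is +0.5 to +2.6 points for R = 0.9 to 0.5.

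**Step 3: simulation of the interval.** The setting was 87 per arm, SD 10, one earlier weight correlated R with Week 72, and 25% missing. Coverage of the nominal 95% interval at R = 0.9/0.8/0.7/0.5 was 0.92/0.89/0.84/0.73 for the difference and 0.95/0.93/0.91/0.85 for the OR. Standard errors were 6–12% too small; most of the loss of coverage is bias. Multiple imputation from the same model gave 64.7–65.0 points, with coverage 0.95–0.96 for the difference and 0.97–0.98 for the OR. At 10% missing, coverage of the difference under the SAP rule was 0.93–0.89.

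**Step 4: simulation closer to the MMRM.** This used 11 weight visits, unstructured covariance, monotone dropout, and correlation over 20 weeks of 0.5/0.7/0.9. With dropout unrelated to outcome, the predicted-value rule gave 72.7/71.1/67.3 points and OR 49.9/43.6/32.5. With poor responders leaving early it gave 67.9–73.0 points and OR 34.8–56.6, against 64.9–66.0 points and OR 26.9–29.4 in the full data. Averaging over the conditional distribution of the missing weight, which is what multiple imputation does, returned 64.6–64.8 points and OR 26.2–26.9 when dropout was unrelated to outcome.

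**Step 5: other responder rates** (closed form, 25% missing, R = 0.9 to 0.5). The difference moves by +0.4 to +1.1 points at 55% vs 90%, 0.0 to +0.6 at 60% vs 90%, and −0.1 to −2.6 at 70% vs 95%. Taking 25% on placebo and an 11-point mean difference, the ≥15% threshold moves by −0.1 to −2.8 points and the ≥20% threshold by −0.5 to −2.8.

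**The case against.** The strongest objection is that the plan's own assumptions do not form one coherent set. Under a normal model with SD 10, 25% vs 90% needs a mean difference of 10 × (1.282 + 0.674) = 19.6 points, not 11. Keeping 11 points and 90% implies 57% on placebo; the bias is then only +0.2 to +0.9 points for R = 0.5 to 0.95, and −8.2 points if every prediction were simply the arm mean. This stands as a limit on size and direction. It does not remove the problem: at 57% vs 90% the odds ratio still rises from 6.7 to between 6.9 and 8.4 over that range of R. Keeping 11 points and 25% instead gives 66.5% on tirzepatide, and the bias is +0.5 to +7.5 points.

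Other points that stand in part:

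- R is unknown, and the most striking figures come from low values. The mechanism is certain; the magnitude is a range.
- The 25% dropout is a planning value, and Protocol 7.2 expects discontinuation to be uncommon. Fewer missing values mean proportionately less bias.
- The odds ratios above are crude, whereas the SAP's model adjusts for four stratification factors and baseline weight. They illustrate the shift and do not predict the reported value. The SAP also does not say how an interval for the difference would be formed.
- That each value is filled in only once is a reading of the SAP's wording, although nothing in it suggests otherwise.
- No decision error follows. With equal arms the responder test alone rejected in 2.4–8.2% of simulations at the 0.025 level, but "superiority of each one of two hypotheses will be declared if and only if both statistical tests" succeed, and both together rejected in 0.8–2.2%.

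**Conclusion.** The concern holds. As written, the rule overstates the ≥5% responder difference and odds ratio at the plan's 25% vs 90% with 25% dropout, for every R below 1. The overstatement is +0.6 to +6.4 points for R from 0.95 to 0.5, with an OR of 28.3 to 45.6 in place of 27.0, and interval coverage below nominal for the difference.

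The size rests on an assumed R, approximate normality and the planned dropout. The direction on the difference scale needs the 5% threshold to lie between the arm means; otherwise the bias is small or can reverse, as it can at the higher thresholds. The superiority conclusion for either dose is unlikely to change. This should be fixed because it distorts the reported estimate and interval of a co-primary endpoint.

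Two minor faults go with it. The change from the protocol's longitudinal logistic regression is missing from SAP 4.9. The NAFLD-improvement row of Table GPHZ.4.2 points to 4.3.2.2, although hepatic fat fraction has one scheduled postbaseline measurement, the case that 4.4.2.2 covers.

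**What to change.** Replace the imputation sentence in SAP 4.3.2.2 with wording such as: missing Week 72 body weight will be multiply imputed (for example, 100 draws, including residual and parameter uncertainty) under the missing-at-random MMRM of Section 4.3.2.1; each completed dataset will be dichotomised and analysed by the logistic model, and the results combined by Rubin's rules.

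Then:

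- apply the same rule to the Week 72 ≥7%, ≥10%, ≥15% and ≥20% thresholds;
- list the departure from Protocol 9.4.3.1 in SAP 4.9;
- redirect the NAFLD-improvement row to 4.4.2.2, and check the IGT-improvement row and the three exploratory rows of Table GPHZ.4.2 that also cite 4.3.2.2, since its fill-in is for body weight.

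The cost is SAP wording and one imputation program; Rubin pooling is already planned for the treatment-regimen estimand. Under the plan's 25% vs 90%, the reported difference and odds ratio become somewhat less favourable and the interval slightly wider. No extra participants are needed and the decision rule is unchanged.

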For the supplemental purpose, sensitivity analysis of the primary efficacy analysis will be performed that will be guided by the "treatment-regimen" estimand and conducted using the FAS, which represents efficacy regardless of adherence to study drug. This assessment will analyze percent change in body weight obtained at the 72-week visit using an analysis of covariance (ANCOVA) and the percentage of participants achieving at least 5% body weight reduction obtained at the 72-week visit using a logistic regression model. Both models will include terms of treatment, stratification factors, and baseline body weight as a covariate. Missing value of change in body weight at the 72-week visit will be imputed based on observed body weight change from baseline values at the visit from participants in the same treatment group who had their efficacy assessed after early discontinuation of study drug. In cases where there are not enough retrieved dropouts to provide a reliable imputation model (for example, the model implemented by the SAS program does not converge), an alternative multiple imputation method with reference to the placebo group (placebo multiple imputation) will be used. Analysis will be conducted with multiple imputations.

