#### 1.1.2.1. Primary estimand

The estimand is described by the following attributes:

- Population: all randomized participants who received at least 1 dose of treatment.
- Endpoint: mean percent change from randomization to Week 72 in body weight, AND percentage of study participants who achieve ≥5% body weight reduction from randomization to Week 72.
- Treatment condition of interest: tirzepatide 10 mg and/or 15 mg QW vs. placebo, excluding data after discontinuation of study drug. Temporary interruptions and modification prior to discontinuation will be allowed as part of the treatment conditions.
- Handling of intercurrent events: the intercurrent events of treatment discontinuation for any reason is addressed by the treatment condition of interest attribute and handled by the hypothetical strategy.
- Population-level summary: difference in mean percent changes between treatment conditions, AND difference in response percentage between treatment conditions.

Rationale for estimand: the estimand aims to reflect treatment efficacy in an envisaged scenario in which the intercurrent events leading to treatment discontinuation would not occur.

This estimand is referred to as 'efficacy' estimand in the latter of this document.

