#### 4. Statistical Analyses

#### 4.1. General Considerations

Statistical analysis of this study will be the responsibility of Lilly or its designee. Any change to the data analysis methods described in the protocol will require an amendment ONLY if it changes a principal feature of the protocol. Any other change to the data analysis methods described in the protocol, and the justification for making the change, will be described in the SAP or the clinical study report. Additional exploratory data analyses may be conducted as deemed appropriate.

Unless otherwise noted, all tests of treatment effects will be conducted at a 2-sided alpha level of 0.05, and the confidence interval will be calculated at 95%, 2-sided. In statistical summaries and analyses, data will be analyzed as randomized.

Unless specified otherwise, efficacy and safety will be assessed using the modified intent-to-treat (mITT) population. Baseline is defined as the last non-missing data collected at randomization (prior to first dosing of study drug). Unless specified otherwise, safety assessments will be guided by an estimand comparing safety of tirzepatide doses with placebo irrespective of adherence to study drug. Thus, safety analysis will be conducted using SS.

Summary statistics for continuous measures will include sample size, mean, SD, median, minimum, and maximum. The analysis model to make comparisons among treatment groups relative to continuous measurements assessed over time will be a mixed model for repeated measures (MMRM), with terms of treatment, visit, and treatment by visit interaction, stratification factors, and baseline measurement as a covariate.

Kaplan Meier method will be used for estimation of cumulative event free survival rates over time, and Cox proportional hazards regression analysis will be used to compare hazard rates among treatments.

Summary statistics for categorical measures (including categorized continuous measures) will include sample size, frequency, and percentages. Logistic regression will be used to examine the treatment difference in binary efficacy outcomes if there is a need to adjust for covariates. Otherwise, Fisher's exact test will be used to examine the treatment difference in categorical outcomes.

Summary statistics for discrete count measures will include sample size, mean, SD, median, minimum, and maximum.

For the safety related parameters, the definition of baseline and postbaseline are specified in Table GPHZ.4.1.

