#### 4.3.1. Definition of endpoints

The primary efficacy measure will be percent change in body weight AND percentage of participants who achieve ≥5% body weight reduction from randomization at 72 weeks. The percent change in body weight at each nominal visit is defined as:

(postbaseline body weight [kg] – baseline body weight [kg]) / baseline body weight [kg] \* 100.

Both percent change in body weight and percentage of participants who achieve ≥5% body weight reduction will be summarized by treatment and nominal visit (week) from randomization to 72 weeks.

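### The estimand for the ≥5% weight-loss co-primary is a difference in response percentage, but the SAP names only an adjusted odds ratio and gives no method for estimating that difference

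*SAP*

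**What the plan says.** Both estimands (SAP 1.1.2.1, efficacy; SAP 1.1.2.2, treatment-regimen) give the population-level summary for the responder endpoint as "difference in response percentage between treatment conditions".

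The analysis sections name something else:

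- **SAP 4.3.2.2 (efficacy estimand).** Logistic regression on treatment, the four stratification factors and baseline weight, yielding a "2-sided 95% CI and odds ratio for percentage of participants achieving at least 5% body weight reduction from baseline to the 72-week visit" for each dose against placebo. Before the fit, "Missing body weight measurement at 72 week will be imputed by the predicted value from MMRM model aforementioned", and the completed weights are dichotomised.
- **SAP 4.3.3.1 (treatment-regimen estimand).** The same closing sentence: "With the aid of the logistic regression model, 2-sided 95% CI and odds ratio for percentage of participants". This section lists no terms for its logistic model. Protocol 9.4.3.1 does, for the ANCOVA and the logistic model alike: "Both models will include terms of treatment, stratification factors, and baseline body weight as a covariate". Missing Week 72 weights are multiply imputed here, with inference by Rubin's rules.
- **SAP 4.3.1.** Both co-primary measures "will be summarized by treatment and nominal visit (week) from randomization to 72 weeks". This is a summary by arm, with no contrast.
- **SAP 4.1.** "Logistic regression will be used to examine the treatment difference in binary efficacy outcomes if there is a need to adjust for covariates". No effect measure is attached.

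Protocol 9.4.3.1 names logistic models without an effect measure. SAP 4.9 lists no change of summary measure.

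**The concern.** An estimand fixes the quantity to be reported, and the analysis section should say how it is estimated and with what uncertainty. For mean percent change the SAP does this: the estimand is a difference in means, and 4.3.2.1 plans a 95% CI for each dose compared with placebo. The responder endpoint is the other half of the same co-primary claim, and its estimand has no stated estimator.

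The odds ratio does not fill the gap. It is adjusted for five covariates, so it is conditional on them, and turning it into a difference in percentages needs the covariate distribution and a stated averaging step. The SAP gives no such step. Two statisticians following it could report different differences with different intervals, or none, and the choice would fall after unblinding. Anyone improvising a difference from the Week 72 data set of 4.3.2.2 would also be working on weights filled in by a single model prediction, which brings a bias of its own.

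**Working it through.** **1. The plan's own figure.** SAP 5 states more than 90% power for the responder comparison, using Fisher's exact test at two-sided 0.025 with 25% against 90%, 87 per arm and 25% dropout. Completers per arm: 87 × 0.75 = 65.25. Enumerating both binomials gives exact power above 99.99% at 65 and at 87 per arm. The statement holds, and nothing below changes it.

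**2. The two quantities at the planning rates.**

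- Difference: 90 − 25 = 65 points.
- Standard error: √[(0.25 × 0.75 + 0.90 × 0.10)/n], which is 5.65 points at n = 87 and 6.53 at n = 65.
- 95% half-width: 1.96 × SE, which is 11.1 and 12.8 points. This is the precision a simple interval would have with complete data. It does not measure an error in the plan.
- Unadjusted odds ratio: (0.90/0.10)/(0.25/0.75) = 9/0.333 = 27.

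An odds ratio alone does not fix the difference. With placebo rate q, the active odds are 27q/(1−q). At assumed q of 10%, 25%, 50% and 70% the implied differences are 65.0, 65.0, 46.4 and 28.4 points.

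**3. What the SAP offers for the difference.**

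| Place | Percentage by arm | Difference | CI for the difference |
|---|---|---|---|
| 1.1.2.1, 1.1.2.2 | – | named as the summary | – |
| 4.3.1 | yes | by hand only | none |
| 4.3.2.2, 4.3.3.1 | – | no method | unclear; only an odds ratio is named |
| 4.1, 4.9 | – | – | – |

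**4. Why the Week 72 data set of 4.3.2.2 cannot simply be reused.** Take percent weight change as normal in each arm, with P(loss ≥5%) equal to 25% and 90%. The standardised thresholds are z = −0.674 and 1.282. Let 25% of Week 72 values be missing at random (the dropout rate in SAP 5). Suppose each is replaced by its prediction from an earlier visit whose change correlates ρ with the Week 72 change. ρ is an assumption, since the documents give none. The predictions have the right mean but only ρ times the SD, so the share of them classed as responders is Φ(z/ρ). The SD itself cancels.

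| ρ | placebo Φ(−0.674/ρ) | active Φ(1.282/ρ) | difference among imputed | shift = 0.25 × (difference − 65) |
|---|---|---|---|---|
| 0.5 | 8.9% | 99.5% | 90.6 | 6.4 points |
| 0.7 | 16.8% | 96.6% | 79.9 | 3.7 points |
| 0.9 | 22.7% | 92.3% | 69.6 | 1.1 points |

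The shift runs in favour of treatment. An interval that treats the predictions as observed would also be too narrow. A simulation of this set-up (4000 trials, 87 per arm) gave a naive SE of 5.16 points against a true SD of 6.09 at ρ = 0.5. Repeating the imputation in bootstrap resamples brings the SE to 5.95 but leaves the 6.4-point shift in place.

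**The case against.** The closing sentence of 4.3.2.2 can be read generously. It speaks of a CI and an odds ratio for a percentage between each dose and placebo, and its counterpart in 4.3.2.1 plainly means a CI for a between-arm difference. On that reading an interval for the percentage contrast is planned and only the wording is loose. This stands in part: the text is ambiguous, so a reader who inferred that the plan rules out any interval for the difference would be going further than the document does. The reading does not close the gap, because no method is given for getting from the logistic fit to a difference.

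It can also be said that superiority under SAP 2 and 2.1 is decided by tests, that arm percentages will be shown, and that 4.3.3.1 is supplementary. All of that is correct, and it limits the consequence to estimation and reporting. A reader might infer that the mismatch undermines the superiority claim or the power. The documents do not support that: a logistic test of no treatment effect bears on the same hypothesis, and the stated power reproduces. Nor can the distance between an unadjusted and an adjusted odds ratio be put forward as the size of the error, since it depends on covariate strengths that the documents do not give.

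A last objection is that the single-prediction problem is a separate matter. In part it is. But it decides how the missing difference can be estimated, and the same filled-in weights feed the odds ratio, its interval and its test, so a remedy for the difference alone would be inconsistent.

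**Conclusion.** The point holds as a gap in estimation and reporting for one co-primary endpoint. The quantity both estimands name has no stated estimator, and the one interval planned is not clearly attached to it. Adding the difference leaves alpha, the stated power and the sample size as they are.

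The gap itself has no size in points. What can be sized is the cost of filling it from the singly imputed data: about 6.4 points too large at a correlation of 0.5, 3.7 at 0.7 and 1.1 at 0.9, on a true 65. Those figures rest on normal weight change, the planning rates, 25% missing at random, a prediction that uses the participant's own earlier data, and a crude difference without covariates. The mismatch of summary measures needs none of these assumptions, because it rests on the text alone.

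**What to change.** **SAP 4.3.3.1.** For each dose against placebo, add the Week 72 difference in response percentage, obtained by averaging the logistic model's predictions over the analysis population under each treatment. Pool estimate and variance over the planned imputations by Rubin's rules, with a 95% CI.

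**SAP 4.3.2.2.** Add the same standardised difference with a 95% CI. Replace the single predicted weight by multiple imputation of missing Week 72 weights under missing at random from the MMRM, using random draws. Dichotomise within each imputation, fit the logistic model and pool by Rubin's rules. Use the same imputed data for the odds ratio and its test. A bootstrap around the single predicted value is not enough, because it repairs the width and leaves the shift.

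**Both sections.** Keep the odds ratio as a further measure and state which quantity each CI is for.

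The cost is some SAP text and extra programming with imputation methods the SAP already uses. No additional participants or data collection are needed.
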